6.1.4. Sample Size Justification for Sensitivity Non-inferiority Analysis

For the sensitivity analysis, the sample size estimation is based on the following assumptions:

- The type I error: $\alpha = 0.05$
- Sensitivity for control test: $Se = 0.85$
- Number of positive patients: $n_1 = 65$
- Non-inferiority margin: $\Delta = 0.10$
- Variability between readers: $\sigma_b^2 = 0.009$
- Variability within the reader: $\sigma_w^2 = 0.00225$
- Correlations: $\rho_1 = 0.46$, $\rho_2 - \rho_3 = 0$
- Correlation: $\rho_b = 0.8$
- Power for the non-inferiority test: $1 - \beta \geq 0.8$

The variance between different patients σ_c^2 will be calculated based on a binomial approximation as follows:

$$\sigma_c^2 = \frac{S_e(1 - S_e)}{n_1}$$

Where S_e is the expected sensitivity and n_1 is the number of positive patients (i.e., patients with cancer).

Philips Mammography Solutions Sweden	Clinical Investigation Plan Comparison of the Philips MicroDose Tomosynthesis System to 2D Digital Mammography	DOC-MTIN-9RWH8K- 8.0 Page 27 of 38
---	---	--

In a previous study on the Philips MicroDose L30 system, the estimated sensitivity was 0.936, with a 95% C.I. (0.897, 0.976) (see Statistics Collaborative, Inc., 2011). In another similar study for the Hologic Tomosynthesis Mammography System, the sensitivity for a 2D system was 0.862 Hologic, Inc. 2012). Based on these previous results, it is expected that the sensitivity for both tests will be approximately 0.85.

In a previous study on Philips MicroDose L30 [19] the estimated σ_b^2 with 95% C.I. was 0.0035 (0.0019, 0.0084). In another similar study for the Hologic Tomosynthesis Mammography System [20] the estimated σ_b^2 with 95% C.I. was 0.0046 (0.0024, 0.0114). Thus a value of 0.009 is a reasonable estimation for σ_b^2 in the proposed study.

The variance within each reader interpreting the results of the same patients σ_w^2 it is assumed to be one-fourth of σ_b^2 , thus 0.0025.

Correlation for the same patients evaluated by the same reader using different tests (ρ_1), for the same patients evaluated by different readers with the same tests (ρ_2) and for the same patients evaluated by different readers and different tests (ρ_3) are based on suggestions from Obuchowski (2000). The correlation for the same reader to evaluate patients using different tests ρ_b ranges from 0.44 to 0.86 in AUC analysis, according to Rockette et al. (1999 such correlation are usually higher for sensitivity analysis. Thus, it is expected that the value ρ_b will be approximately 0.80 for this study.

Based on these assumptions, for the sensitivity analysis, 18 readers will be required to achieve statistical power of at least 0.80, after adjusting for multiple endpoints.

6.1.5. Sample Size Justification for Specificity Non-inferiority Analysis

For specificity analysis, similar to sensitivity analysis, the following assumptions were made:

- The type I error: $\alpha = 0.05$
- Specificity for control test: $S_p = 0.70$
- Number of positive patients: $n_2 = 300$
- Non-inferiority margin: $\Delta = 0.10$
- Variability between readers: $\sigma_b^2 = 0.012$
- Variability within the reader: $\sigma_w^2 = 0.003$
- Correlations: $\rho_1 = 0.46$, $\rho_2 - \rho_3 = 0$
- Correlation: $\rho_b = 0.8$
- Power for the non-inferiority test: $1 - \beta \geq 0.8$

Similar to sensitivity analysis, the variance between different patients σ_c^2 will be calculated based a binomial assumption, as described above.

In a previous study on the Philips MicroDose L30, the estimated specificity was 0.764, with a 95% C.I. (0.688, 0.841) [19]. In another similar study for the Hologic Tomosynthesis Mammography System, the specificity for a 2D system was 0.651 [20]. Based on these previous results, it is assumed that the specificity for the control test is approximately 0.70.

Also, in a previous study on Philips MicroDose L30 [19], the estimated σ_b^2 with 95% C.I. was 0.0087 (0.0047, 0.0208). In another similar study for the Hologic Tomosynthesis Mammography System [20], the estimated σ_b^2 with 95% C.I. was 0.0144 (0.0077, 0.0357). Thus a value of 0.012 is a reasonable estimation for σ_b^2 for the proposed study.

The variance within each reader interpreting the results of the same patients σ_w^2 is estimated as one-fourth of σ_b^2 , thus 0.003.

Philips Mammography Solutions Sweden	Clinical Investigation Plan Comparison of the Philips MicroDose Tomosynthesis System to 2D Digital Mammography	DOC-MTIN-9RWH8K- 8.0 Page 28 of 38
---	---	--

Correlation for the same patients evaluated by the same reader using different tests (ρ_1), for the same patients evaluated by different readers with the same tests (ρ_2) and for the same patients evaluated by different readers and different tests (ρ_3) are based on suggestions from Obuchowski [11]. The correlation for the same reader to evaluate patients using different tests ρ_b ranges from 0.44 to 0.86 in AUC analysis, according to Rockette [18] such correlation are usually higher for sensitivity/specificity analysis. Thus, it is safe to assume the expected value ρ_b to be 0.80 in the proposed study.

Based on these assumptions, for the specificity analysis, 18 readers will be required to achieve statistical power of at least 0.80, after adjusting for multiple endpoints.

6.2. General Statistical Considerations

The primary analysis will be performed including all subjects selected for the reading portion of the study with confidence score for both Philips MicroDose tomosynthesis system and FFDM evaluation (modified intent to treat, MITT). For this analysis patient will be the basis for the analysis. Non-cancer cases, with missing one year follow-up will be assumed as cancer free case. Missing values will be assumed to be missed at random.

The analysis of safety includes all enrolled subjects in the acquisition portion of the study.

Continuous variables will be summarized using the number of non-missing observations, mean, standard deviation, 95% Confidence Interval (CI) for the mean, median, minimum, and maximum; categorical variables will be summarized using the frequency count and the percentage of subjects in each category. Analyses will be conducted using SAS® software and OR-DBM MRMC software [12].

6.3. Subject Disposition

Subject disposition, including total screened, enrolled in the acquisition and reading portion of the study, early terminations and withdrawals, will be presented. In addition, a listing will be provided with the reasons for discontinuation.

6.4. Demographics and Baseline Characteristics

Standard subject baseline characteristics (e.g., age, race and origin) will be summarized for all subjects enrolled in the imaging acquisition and imaging reading portion of the study. For continuous subject characteristics, means, standard deviation, median and range will be provided. The number of events and percentage of events will be presented for all categorical variables.

6.5. Readers Compliance

Reader compliance will be listed by image type. If applicable, comparability between the two image types (i.e., Philips MicroDose tomosynthesis system and FFDM) groups will be evaluated using a Chi-square or Fisher's exact test as appropriate. A listing of all deviations will be presented.

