5.4.2.3. Matching Reader Indicated Lesion Locations to Truth

For all cancer cases, the lesion location(s) provided by the readers will be assessed for correspondence to the known cancer locations. For purposes of analysis, the cases which the reader assigns a score of BI-RADS 3 or higher and which correspond to the known cancer location (as described below) will be considered as correctly localized.

5.4.2.4. Correct Localization:

A reader will get credit for correct localization of a cancerous lesion if the laterality matches the true laterality of the cancer and any of the three rules below apply:

- Reader recorded lesion at a specific o'clock location anywhere from 1 to 12 is the same as the o'clock location documented by the truther within 2 o'clock ticks.
- Lesions indicated by the truther as being located in the Subareolar region that is reported as Subareolar by the reader.
- Lesions indicated by the truther as in the Axillary Tail region must be reported in either the Axillary Tail or 10, 11, or 12 o'clock (right breast) or 12, 1, 2 (left breast) by the reader.

5.4.3. **Case selection - Image Reading**

Cases for the reader study will be selected from all of the cases acquired through the case acquisition phase. A total of approximately 65 cancers, 40 cases with benign biopsies and 300 normal cases will be selected in sequential order to fulfill the requirements for case stratification. The 300 normal cases will include some cases that were recalled from screening but ultimately determined to be normal after additional work-up, as well as cases that were not recalled from screening. Approximately 10% additional cases will be included to protect from loss to follow-up prior to 1 year status verification.

Case stratification is described in detail in 5.4.6. In summary, cancer cases will be stratified by lesion type and size, and breast density. Benign cases will be stratified by lesion type and breast density. Normal cases will be stratified by breast density and by the recommendation for additional work-up after screening. Once the target case number is reached data collection will stop.

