Approximately 18 American Board of Radiology (ABR) certified and Mammography Quality Safety Act (MQSA) qualified radiologists will review and score the cases according to Image Review methods described Image Reading, Section 5.4.2. All readers will undergo training on interpretation using the Philips MicroDose tomosynthesis system images to become familiar with the images and the review workstation to be used in the study.

To avoid recall bias, the reading will be divided in two sessions structured using a crossover design with a washout period of one month between sessions as presented in Figure 3.

[figure not shown]

Figure 3: Reading Scheme

Philips Mammography Solutions Sweden	Clinical Investigation Plan Comparison of the Philips MicroDose Tomosynthesis System to 2D Digital Mammography	DOC-MTIN-9RWH8K- 8.0 Page 19 of 38
---	---	--

Each reader will independently review 2D mammograms and MicroDose images (i.e., Tomosynthesis and synthetic 2D) of the same patient in separate sessions to minimize memory effects. The cases will be randomly divided into two groups, Group A and Group B. In the first reading session, the readers will read Group A with modality 1 and Group B with modality 2. In the second reading session, the readers will read Group A with modality 2 and Group B with modality 1. Within each reading session, the order in which the cases will be read will be randomized to avoid confounding the device effect with reading order effects.

Each reading session may be divided into several visit times to adapt to the readers' schedule. Furthermore, to avoid bias, no patient history or other clinical information will be provided to the reader.

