6. STATISTICAL CONSIDERATIONS

6.1. Sample Size and Number of Readers Justification

6.1.1. Sample Size Justification for Primary Efficacy Analysis

The primary endpoint is the Receiver Operator Characteristics curve analysis for both tests. In this trial, the 2D is the control test, and the tomosynthesis and synthetic 2D is the experiment test. The plan is to enroll approximate 800 patients, to include 65 patients with cancer, 40 biopsy-proven benign cases and 300 normal cases. The evaluations will be based on paired-cases and paired-readers that is all readers will interpret the test results of all patients in both tests (i.e., Philips MicroDose tomosynthesis system and FFDM).

The sample size (number of readers) for the Reader Study is estimated based mixed-effects model for the diagnostic accuracy of a reader j using a particular diagnostic test i on reading occasion q as proposed by Obuchowski [11]. The mixed model is specified as follows:

$$\hat{\theta}_{ijq} = \mu + \mu_i + r_j + (ur)_{ij} + \epsilon_{ijq}$$

Here, $v_i = \mu + \mu_i$ is the mean accuracy of test i (fixed effect), r_j is a random effect for reader j , $(ur)_{ij}$ is an interaction term for readers and tests (random effect), and ϵ_{ijq} is an error term.

An F-statistic with 1 and $(J-1)$ degree of freedom (df) will be used for testing the null hypothesis that the mean diagnostic accuracies of the tests are equal, where J is the number of readers. Under alternative hypothesis, the test statistic follows a non-central F distribution with 1 and $(J-1)$ df, and the non-centrality parameter is estimated as following:

$$\hat{\lambda} = \frac{J(\mu_1 - \mu_2)^2}{2\{\hat{\sigma}_b^2(1 - \hat{\rho}_b) + \frac{\hat{\sigma}_w^2}{Q} + \hat{\sigma}_c^2[(1 - \hat{\rho}_1) + (J - 1)(\hat{\rho}_2 - \hat{\rho}_3)]\}}$$

Philips Mammography Solutions Sweden	Clinical Investigation Plan Comparison of the Philips MicroDose Tomosynthesis System to 2D Digital Mammography	DOC-MTIN-9RWH8K- 8.0 Page 25 of 38
---	---	--

Thus, to calculate the statistical power, multiple parameters in the equation above need to be estimated. For this study, these estimates are based on the following assumptions:

- The type I error: $\alpha = 0.05$
- AUC for control test: $A = 0.85$
- Number of positive patients: $n_1 = 65$
- Number of negative patients: $n_2 = 300$
- Non-inferiority margin: $\Delta = 0.05$
- Variability between readers: $\sigma_b^2 = 0.0009$
- Variability within the reader: $\sigma_w^2 = 0.000225$

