6.6. Primary Efficacy Analysis

The primary objective of the study is to compare the clinical performance of the Philips MicroDose tomosynthesis system (tomosynthesis with a synthetic 2D) images and 2D FFDM system. The primary endpoint is the Area under the ROC curve (AUC) using patient as the unit of analysis. The ROC curves will be generated using the confidence scores (1 to 100) and the reference standard (i.e., normal/benign or cancer). All subjects with both Philips MicroDose tomosynthesis system and FFDM evaluation (modified intent to treat, MITT). For subjects with negative outcome for whom a 1 year follow-up is required, missing values will be removed from the study database.

Smooth ROC curves and area under the curve will be estimated from the CS for each study reader interpreting images acquired with the Philips MicroDose tomosynthesis system and the FFDM

Philips Mammography Solutions Sweden	Clinical Investigation Plan Comparison of the Philips MicroDose Tomosynthesis System to 2D Digital Mammography	DOC-MTIN-9RWH8K- 8.0 Page 29 of 38
---	---	--

systems. If smooth ROC curves cannot be fitted for each reader in each condition (e.g., if there is perfect performance), nonparametric methods may be used. Results will be summarized across readers using the method of [10] which includes random effects for study readers and uses the jackknife to handle correlation within cases, as obtained in the corresponding OR-DBM MRMC software. Robustness of the statistical method may be explored through use of the ANOVA model of Obuchowski and Rockette [11]; this model includes random effects for study readers, and adjusts variances and hypothesis tests for correlations due to having each reader interpret the same case sample. The degrees of freedom may be adjusted as suggested by Hillis [14]. The average AUC for Philips MicroDose tomosynthesis system and the FFDM, the average difference between the two systems, and its standard error for use in computing confidence interval and to performing hypothesis tests for the difference will be estimated.

The following hypothesis will be evaluated:

- Null Hypothesis: $H_0: \Theta_2 - \Theta_1 \geq 0.05$
- Alternative Hypothesis: $\Theta_2 - \Theta_1 < 0.05$

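### Section 6.5 compares reader compliance between image types with tests for independent groups, although the same readers read the same cases in both, so the p-value does not hold its nominal level

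*Combined protocol and SAP*

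**What the plan says.** Section 6.5 lists reader compliance by image type. Where applicable, it then tests "comparability between the two image types (i.e., Philips MicroDose tomosynthesis system and FFDM"); the two "groups will be evaluated using a Chi-square or Fisher's exact test as appropriate". It also promises a listing of all deviations. It does not say what counts as compliance, whether the unit is the reader, the session or the single read, or what significance level applies.

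The design is set out elsewhere. Section 6.1.1 describes "paired-cases and paired-readers that is all readers will interpret the test results of all patients in both tests". Section 5.4.3 says: "Each reader will independently review 2D mammograms and MicroDose images (i.e., Tomosynthesis and synthetic 2D) of the same patient in separate sessions". The same section plans about 18 readers and, for the case set, "A total of approximately 65 cancers, 40 cases with benign biopsies and 300 normal cases will be selected".

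Other analyses in the plan allow for this structure. In section 6.6 the primary AUC method has random reader effects and handles correlation within cases, and the Obuchowski-Rockette model, named there as a robustness analysis, "adjusts variances and hypothesis tests for correlations due to having each reader interpret the same case sample". Section 6.8 uses a paired binomial test within reader for sensitivity and specificity, and a clustered binary method for recall.

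**The concern.** The Pearson chi-square and Fisher's exact tests compare two independent samples. Here each observation on one image type has a partner on the other, from the same reader and, at read level, the same case. Reads by one reader may also resemble each other. Neither feature enters the planned test.

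What is at stake is modest. The primary analysis set in sections 6.2 and 6.6 keeps subjects evaluated on both systems, so a difference between modalities in missing or deviant reads bears on how the primary comparison is interpreted. Section 6.5 holds the only statistical comparison of compliance in the plan. A p-value off its nominal level could make a real imbalance look unremarkable or, under a further condition shown below, raise a false alarm.

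**Working it through.** The plan states no expected rate, power or level for this comparison, so there is no figure to reproduce. The check has three parts.

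**Inputs from the documents.** About 18 readers (5.4.3); 65 + 40 + 300 = 405 cases (5.4.3); all readers read all cases in both tests (6.1.1). If the unit is the read, that makes 18 × 405 = 7,290 reads per image type, from the same reader-case pairs.

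**Assumptions, none of them in the documents.** The unit is the read; the test is two-sided at 5%; p is a common non-compliance rate; the correlations are as given below.

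**1. Formula at read level.** Let n = 7,290. The unpaired test takes the variance of the difference in rates as 2p(1−p)/n. Define:
- ρ: correlation between the two reads of one reader-case pair;
- a: correlation between different cases read by one reader in different modalities;
- a + d: the same correlation within one modality, so d measures reader-by-modality variation;
- c: correlation between readers on the same case, equal within and across modalities.

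Each modality mean has variance [p(1−p)/n] × [1 + 404(a + d) + 17c]. The covariance of the two means is [p(1−p)/n] × [ρ + 404a + 17c]. Subtracting, the true variance of the difference is

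2p(1−p)/n × F, with F = 1 − ρ + 404d.

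The common reader term a and the common case term c drop out. The actual error rate is 2[1 − Φ(1.96/√F)].

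- ρ = 0.3, d = 0: F = 0.7, 1.96/√0.7 = 2.34, error 1.9%.
- ρ = 0.5, d = 0: F = 0.5, 1.96/√0.5 = 2.77, error 0.6%.
- Additive reader effect only (ρ = a = 0.01, d = 0): F = 0.99, error 4.9%. Common reader clustering does not inflate the error.
- The error exceeds 5% only if 404d > ρ, that is d > 0.3/404 = 0.0007 at ρ = 0.3, or d > 0.5/404 = 0.0012 at ρ = 0.5.

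**2. Simulation at read level.** The design of 18 readers, 405 cases and 2 modalities was simulated with no true modality difference (latent probit model, total variance 1, 1,500 runs per setting). Non-compliance rates and variance components are assumed. The table gives rejection rates at nominal 5%, for 2% / 5% non-compliance.

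| Setting | Unpaired chi-square | McNemar |
|---|---|---|
| Independent reads | 5.0% / 6.0% | 4.9% / 6.1% |
| Moderate shared correlation (reader 0.1, case 0.2, reader-case 0.2) | 3.3% / 2.1% | 5.1% / 4.7% |
| Strong shared correlation (0.2, 0.3, 0.3) | 0.8% / 0.7% | 4.4% / 5.8% |
| Moderate, plus reader-by-modality variance 0.02 | 19% / 26% | 23% / 31% |
| Moderate, plus reader-by-modality variance 0.10 | 51% / 62% | 53% / 65% |

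The direction agrees with part 1. Simple McNemar on reads repairs the pairing but not the reader-by-modality variation.

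**3. Reader as the unit.** Suppose 12 of 18 readers have a deviation on one image type and 5 of 18 on the other, with 7 discordant readers all in one direction. Fisher's test gives p = 0.044 and exact McNemar gives p = 2 × 0.5⁷ = 0.016. In simulation with 30% of readers deviating and latent correlation 0, 0.5 and 0.8, Fisher rejected in 2.2%, 0.6% and 0.1% of runs under no difference. Exact McNemar rejected in 1.8%, 0.9% and 0.2%; with 18 readers it is also conservative, because it is discrete.

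**The case against.** The strongest reply is that nothing depends on this test. It is conditional, it is absent from the gatekeeping table in section 6.8 and from every sample size calculation in section 6.1, and no inclusion rule uses it. That stands, and it caps the importance of the point.

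A second reply is that the word chi-square could cover McNemar's test. That is possible, but naming it beside Fisher's exact test and speaking of groups points to the independent-samples version. If McNemar was meant, the text should say so, and on reads it would still fail under reader-by-modality variation.

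A third reply is that the unit is undefined and all correlations are assumed. This is also true. It limits what can be said about size, but the independence assumption fails whether the unit is the reader, the session or the read.

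A reader might also infer three stronger things that the documents do not support:
- That clustering by reader in itself makes the test reject far too often, through a design effect of 1 + 404 × ICC. That formula fits different readers in each modality. Here the readers are the same, so an effect common to both modalities cancels.
- That this test is the plan's sole safeguard against unbalanced missing or deviant reads. Section 6.5 also lists compliance by image type and all deviations, and section 5.5.2 has a research associate check for missing items and query them before a reader ends a session.
- That the plan sets out to treat 7,290 reads per modality as independent. The read is only one possible unit; section 6.5 does not name one.

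**Conclusion.** The point holds as a minor error in a stated analysis. The tests named in section 6.5 assume independent groups, the crossed design rules that out, and the resulting p-value does not hold its nominal level. The plan handles the same dependence properly for AUC, sensitivity, specificity and recall.

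The size is illustrative only. Per read, with an assumed within-pair correlation of 0.3 to 0.5 and no reader-by-modality variation, the nominal 5% test runs at about 1.9% to 0.6%. With enough reader-by-modality variation the error goes the other way. The documents do not show which case applies, so no net direction can be claimed. The primary and secondary conclusions of the trial do not rest on this comparison.

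**What to change.** In section 6.5, first define reader compliance and its unit. Then choose one of two courses:

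- Replace the chi-square/Fisher test with a paired comparison at reader level. Compute each reader's compliance rate on each image type and compare the approximately 18 within-reader differences by signed-rank or paired t test. If compliance is yes/no per reader, use exact McNemar. The comparison of differences respects both the pairing and reader-by-modality variation, taking the case set as fixed.
- Report compliance by image type descriptively, with the deviation listing already planned and no p-value.

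A GEE logistic model clustered by reader is not advised unless it carries a small-sample correction for 18 clusters; it would also ignore correlation between readers on the same case.

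The cost is a sentence or two in the plan and trivial programming. No extra data are needed.
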